We have access to a large (N>70) and unique population of individuals with SCI who have been enrolled in FESRT for at least 6 months. Roughly half have high level SCI between C4 and T4.

II. SPECIFIC AIMS

Aim 1: To determine the magnitude of improvement in aerobic capacity after 3 months of FESRT+NIV compared to FESRT+shamNIV in high level spinal cord injury.

Aim 2: To examine the relationship among gains in ventilation and increases in the determinants of aerobic capacity - maximal cardiac output and arterio-venous oxygen difference after 3 months of FESRT+NIV in high level spinal cord injury.

Aim 3: To examine the acute effect of NIV on FES-row VO₂max in subjects with both high and low level SCI.

III. SUBJECT SELECTION

FES-Row-Training Group

Thirty individuals with high level SCI who have FES-row trained for at least 6 months will be randomized to (continued) FESRT for 3 months with either NIV or sham NIV. Patients will be medically stable and inclusion criteria are SCI at neurological level \geq T4 with American Spinal Injury Association grade A or B or C, aged \geq 18 years of age. Before and after training, we will assess maximal aerobic capacity, ventilation, cardiac output, and arterio-venous oxygen difference. Based on our current data, we hypothesize that only those randomized to NIV will experience further increases in aerobic capacity and that these increases will relate to increased cardiac output and arterio-venous oxygen difference. This project will determine the feasibility and effectiveness of this approach to exercise and will lay the groundwork for a larger study of the impact of FESRT+NIV to improve health and function in those with high level SCI.

FES-Row-Exercise Testing Only Group (Cross-Sectional)

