FES-Row Training. The FES row system will optimize the contribution of the pre-trained muscle components of quadriceps and hamstrings. To maintain the proper training stimulus at the same relative intensity, a maximum FES-rowing test will be performed at baseline for intensity to be determined. The goal is for each volunteer to achieve an exercise intensity of 75-85% maintained for at least 30 minutes performed three times each week. Measurements of force produced at the foot and handle during FES-row training sessions will also be used to monitor training and possibly improve rowing technique. Subjects exercise programs will be tailored specifically to their fitness level but should progress quickly to the prescribed intensity as all subjects

There is no limit or specific requirement for training sessions that must be attended to continue participating in this protocol. Subjects will be encouraged by study staff to attend three training sessions per week. Un-reported missed training session will be followed up with a phone call to document why the training session was missed and to encourage prompt return to training sessions as soon as possible.

Strength Training during FES-RT

As subjects will already have been participating in FES-row training they will also be given the opportunity to continue or start the FES-leg strength training at home concurrently on non FES-rowing days (~3 days/week, 30-60 minutes/session). This will be possible after the subjects have demonstrated the knowledge and ability of proper use of the stimulation unit for home use. This will be

closely monitored, as they will also be FES-rowing three times per week at Spaulding Cambridge.

Study Assessments

FES-Row Training Group

All Assessments will be performed at baseline and after three months of FES-row training. There will be 2 separate FES-VO₂max row tests, 2 separate Cardiac Output row tests and 1 Pulmonary Function test done at each time point (done at least 48-hours apart). Both NIV Support and Sham-NIV groups will perform tests with and without use of the NIV-machine.

FES-Row Exercise Testing Only Group

Subjects will perform FES-VO₂max row tests on separate days with and without the use of NIV to determine maximal aerobic capacity and ventilation. Both FES-VO₂max Row tests will be performed at least 48-hours apart

Measurements and Testing Protocols:

FES-Row-VO₂max Testing

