Individuals will refrain from eating for 2 hours prior, from caffeine and alcohol for 24 hours prior, and from vigorous physical activity for 48 hours prior to testing. Aerobic power will be determined from online computer-assisted open circuit spirometry and expired gas analysis will be performed continuously throughout the test with the Innocor rebreathing system (Innovision, Odense, Denmark, see details below). A heart rate monitor (Suunto, [name]) will be used throughout the tests. The baseline graded FES row test protocol will be based on each individual's initial FES row response, and 1- to 2-minute workloads will be selected to achieve test protocols of 8 to 12 minutes of incremental exercise. The same protocol will be used for the 3-month posttest unless the initial workload has become too low to allow proper FES rowing technique. In this case, the initial workload will be the second workload from the pretest. To ensure attainment of peak exercise capacity, at least 3 of the following criteria must be met: 85% of age predicted maximal heart rate ($220 - \text{age}$), respiratory exchange ratio >1.1 at end exercise, plateau in oxygen consumption despite increasing workload, blood lactate level (Lactate Plus, Nova Biomedical, Waltham MA) of 8 mM or above, rating of perceived exertion of at least 17 on the Borg scale of 6 to 20, and precipitous decline in power $>20\text{W}$ during maximal leg stimulation. Peak oxygen consumption will be defined as the highest value achieved over 30 seconds.

Immediately after FES-rowing has stopped at the end of the VO₂max test, subjects will have a finger tip pricked with a safety lancet in order to get a drop of blood that will be used to measure peak lactate levels in whole blood. Peak lactate levels will be used to evaluate exercise intensity as well as to monitor training status.

Cardiac Output Row Testing

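### Participants in either arm may start home FES-leg strength training during the NIV versus sham comparison, and neither the design nor the analysis accounts for it

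*Combined protocol and SAP*

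**What the plan says.** Section III (FES-Row-Training Group) randomises thirty people who have already rowed for at least six months to three more months of rowing with NIV or sham NIV. Both arms row; only the ventilatory support is randomised. The stated expectation there is: "we hypothesize that only those randomized to NIV will experience further increases in aerobic capacity".

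Section V (FES-Row Training) sets the rowing target: "The goal is for each volunteer to achieve an exercise intensity of 75-85% maintained for at least 30 minutes performed three times each week". Attendance is encouraged, but no minimum is required.

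Section V (Strength Training during FES-RT) then adds an optional home programme for the same people over the same period: "they will also be given the opportunity to continue or start the FES-leg strength training at home concurrently on non FES-rowing days". The one condition is competence with the equipment: "This will be possible after the subjects have demonstrated the knowledge and ability of proper use of the stimulation unit". The section promises close monitoring. It does not describe a log, a rule that holds earlier habits steady, or stratification by strength-training status.

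Section V (Sham-NIV) states that participants are blinded to their group and to the level of support. It does not say whether staff are blinded.

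Section VI compares changes within and between groups with a general linear model that covers baseline differences and the intervention effect. It also plans correlations between ventilation, aerobic capacity, cardiac output and arteriovenous oxygen difference. Home strength training appears in neither analysis.

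**The concern.** Continuing an established habit is a pre-randomisation characteristic, which randomisation balances in expectation. Starting a new programme is a choice made after randomisation. It brings a new stimulus to the legs, the same limbs that FES rowing works, and it overlaps with the period over which the endpoint is measured.

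Three inferences are exposed, to different degrees.

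- **Aim 1, between arms.** If new starts are more common in one arm, the difference in aerobic capacity mixes the effect of NIV with the effect of strength training. If they are equally common, they only add variability.
- **The hypothesis that only the NIV arm gains.** This is a within-arm statement. New starters in the sham arm could produce a gain that has nothing to do with NIV, even when uptake is equal.
- **Aim 2.** The relation between ventilation gains and cardiac output or oxygen extraction after FESRT+NIV is a within-arm correlation, so randomisation does not protect it. Stimulated leg training could plausibly change oxygen extraction without changing ventilation.

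**Working it through.** **1. Amount of home training offered.** From section V: rowing is "maintained for at least 30 minutes performed three times each week", and home training takes place "on non FES-rowing days (~3 days/week, 30-60 minutes/session".

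- Rowing minimum: 3 × 30 = 90 min/week.
- Home strength: 3 × 30 to 3 × 60 = 90–180 min/week.
- Ratio at the rowing minimum: 90/90 to 180/90 = 1.0–2.0.

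The rowing figure is a floor. With 60-minute rowing sessions (180 min/week) the ratio is 0.5–1.0. With two of three 30-minute sessions attended (60 min/week) it is 1.5–3.0. Minutes of strength work and minutes of rowing are not equivalent doses, so this shows only that the co-intervention is not trivial.

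**2. Reference power.** Section VI gives a significance level of 0.05 and power of 80% but no effect size or SD, so N = 30 cannot be reproduced. Assuming 15 per arm and a two-sided test, the detectable difference is (1.960 + 0.842) × √(2/15) = 1.02 SD by the normal formula, or 1.06 SD by the t-test. The value 1.06 SD is the reference below.

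**3. Effect on Aim 1.** The documents give neither the uptake nor its effect on aerobic capacity; both are assumed. Let strength training add *e* SD to the change, with uptake p(NIV) and p(sham). The expected shift in the arm difference is e × [p(NIV) − p(sham)]. Simulated two-sample t-tests (40,000 runs) gave:

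| Uptake NIV / sham | e (SD) | Expected shift (SD) | Type I error | Power at 1.06 SD |
|---|---|---|---|---|
| none | – | 0 | 0.05 | 0.80 |
| 50% / 50% | 0.5 | 0 | 0.05 | 0.78 |
| 50% / 50% | 1.0 | 0 | 0.05 | 0.71 |
| 70% / 30% | 0.5 | 0.4 × 0.5 = +0.20 | 0.08 | 0.90 |
| 70% / 30% | 1.0 | 0.4 × 1.0 = +0.40 | 0.16 | 0.94 |
| 30% / 70% | 0.5 | −0.20 | 0.08 | 0.60 |
| 30% / 70% | 1.0 | −0.40 | 0.16 | 0.35 |

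The equal-uptake rows follow from the added variance. At 50% uptake it is e² × 0.5 × 0.5, so the SD rises from 1 to √1.0625 = 1.03 (e = 0.5) or √1.25 = 1.12 (e = 1.0). A smaller *e* costs less, and e = 0 costs nothing.

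**4. Chance imbalance.** With the same uptake probability in both arms (exact binomial, 15 per arm), a gap of four or more users has probability 0.11 at 20% uptake, 0.16 at 30% and 0.20 at 50%. A gap of four moves the contrast by (4/15) × e, which is 0.07 SD at e = 0.25 and 0.27 SD at e = 1.0.

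**5. Sham-arm gain with equal uptake.** If 30–50% of the sham arm start and e is 0.5–1.0 SD, the sham mean rises by 0.3 × 0.5 = 0.15 SD to 0.5 × 1.0 = 0.50 SD, with no contribution from NIV.

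**The case against.** The strongest reply is blinding. Participants do not know their arm and both arms get the same offer, so uptake may well be unrelated to treatment. In that case type I error is unchanged and only power suffers. This stands, and it rules out the stronger reading that the home programme by itself breaks the attribution of the Aim 1 difference to NIV. The documents do not show differential uptake. Blinding does not exclude it, however. Section I expects NIV to improve exercise tolerance, which could alter willingness to add sessions. Staff blinding is not stated, and someone has to judge competence before home use begins.

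A reader might also treat the chance gaps in step 4 as bias. They are ordinary sampling variability, already reflected in the standard error. Large gaps are also uncommon: six or more users has probability about 0.04 at 50% uptake. Step 4 further treats every participant as a possible starter, although some may already do home training.

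The assumed effect can fairly be challenged. Section I argues that ventilation limits aerobic capacity in this population, and section V describes the thigh muscles as already trained, so extra leg work may add little. The range for *e* should be read as reaching down to zero.

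Finally, one might infer a scheduling conflict with the requirement to refrain "from vigorous physical activity for 48 hours prior to testing". The documents do not support that. The restriction is stated for the VO₂max and cardiac output tests (four per time point), not for the pulmonary function test. No section classes home sessions as vigorous, and testing takes place at baseline and after three months. That argument forms no part of this point.

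**Conclusion.** The point holds as a weakness in design and analysis that is cheap to remove. It is not a demonstrated bias. The plan lets a new leg-training stimulus, 90–180 min/week against a rowing floor of 90 min/week, begin during the randomised comparison, and the analysis ignores it.

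If uptake is unrelated to arm, the cost to Aim 1 is power: 0.80 falls to 0.78 or 0.71 for an effect of 0.5 or 1.0 SD at 50% uptake, and by less for a smaller effect. If uptake differs by arm, Aim 1 could be biased in either direction, with type I error of about 0.08–0.16 at 70% versus 30%. The within-arm hypothesis and the Aim 2 correlations are exposed even when uptake is equal.

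All these sizes rest on assumptions: 15 per arm, a two-sided test, and invented values for uptake and effect. The text supports saying that the home programme can distort the results, not that it will.

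**What to change.** 1. In section V (Strength Training during FES-RT), delete the option to start for the duration of the three-month comparison. Existing users carry on their usual practice; others are offered the programme after their three-month assessments.
2. At the screening session, before randomisation, record home strength-training status (yes/no). Name it in section VI as a baseline covariate in the Aim 1 model.
3. Turn the promised monitoring into a log of home sessions and report it by arm. Use it only in a prespecified sensitivity analysis. It should not be a covariate in the primary model, because post-randomisation training may itself be affected by the assigned arm.

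**Cost.** A few sentences of protocol text, one screening item and a simple log. Non-users wait three months for an optional programme. That might slightly affect recruitment, since section I puts the available population at more than 70, roughly half with high-level injury, which is somewhat over 35 candidates for 30 places. The model loses one degree of freedom: with an intercept, arm and one baseline value, residual degrees of freedom go from 30 − 3 = 27 to 26.

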Individuals will refrain from eating for 2 hours prior, from caffeine and alcohol for 24 hours prior, and from vigorous physical activity for 48 hours prior to testing. Cardiac output will be measured at rest and during a three to six minute FES-row steady state exercise bout at an intensity of 80% of peak heart rate. Cardiac Output is measured using the inert gas re-breathing method (Innocor, Innovision, Odense, Denmark), a previously validated non-invasive method for rest and exercise measures. Notably, inert gas re-breathing measurements of cardiac output do not require steady state conditions and hence can be

obtained during graded tests. An oxygen-enriched mixture of an inert soluble gas (0.5% nitrous oxide) and an inert insoluble gas (0.1% sulphur-hexafluoride) are used to indirectly assess pulmonary blood flow and lung volume, respectively. In the absence of pulmonary shunt, cardiac output = pulmonary blood flow. Arteriovenous oxygen difference will be derived by applying the Fick principle: arteriovenous oxygen difference = oxygen consumption / cardiac output. Subjects will do 2 re-breathing maneuvers at rest and 2 re-breathing maneuvers once they have achieved target heart rate.

Pulmonary Function Tests

Spirometry will be used to measure lung function, specifically the measurement of the amount (volume) and/or speed (flow) of air that can be inhaled and exhaled. Specifically, Forced Volume Vital Capacity (FVC) and Maximum Voluntary Ventilation (MVV) tests will be administered.

Regional Cerebral Blood Flow

A Near-Infrared Spectroscopy (NIRS; PortaLite, Artinis Medical Systems) probe placed on the forehead contralateral to the dominant hand will be used to measure blood oxygenation during maximal exercise testing. NIRS-derived blood oxygenation levels will be used as a measure of cerebral blood flow at the prefrontal cortex.

VI. BIOSTATISTICAL ANALYSIS

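### Aim 2 is about maximal cardiac output, but the only exercise cardiac output measurements scheduled are at 80% of peak heart rate

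*Combined protocol and SAP*

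**What the plan says.** In section II, Aim 2 names the determinants of aerobic capacity to be related to gains in ventilation: "maximal cardiac output and arterio-venous oxygen difference after 3 months of FESRT+NIV in high level spinal cord injury". Section III lists the before-and-after assessments for the training group: "we will assess maximal aerobic capacity, ventilation, cardiac output, and arterio-venous oxygen difference".

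Section V, Study Assessments, keeps the cardiac output tests separate from the two VO₂max tests: "2 separate Cardiac Output row tests and 1 Pulmonary Function test done at each time point". The Cardiac Output Row Testing section then sets the conditions. Cardiac output is taken at rest and "during a three to six minute FES-row steady state exercise bout at an intensity of 80% of peak heart rate", and the manoeuvres are counted: "Subjects will do 2 re-breathing maneuvers at rest and 2 re-breathing maneuvers once they have achieved target heart rate". The arteriovenous difference is calculated, not measured: "arteriovenous oxygen difference = oxygen consumption / cardiac output".

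Two sentences point towards the graded test. Under FES-Row-VO₂max Testing, "expired gas analysis will be performed continuously throughout the test with the Innocor rebreathing system", with a pointer to details further down. Under Cardiac Output Row Testing, "inert gas re-breathing measurements of cardiac output do not require steady state conditions and hence can be" introduces the statement that such measurements are obtainable in graded tests.

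Section VI plans Pearson or Spearman correlations among ventilation, aerobic capacity, cardiac output and arteriovenous difference. It does not say whether the resting or the exercise values are used.

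**The concern.** The quantity named in Aim 2 is not the quantity the procedure produces. Aerobic capacity in this plan is a peak value, so its determinants in the sense of Aim 2 are cardiac output and oxygen extraction at peak. The cardiac output test stops short of peak by design.

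At stake is what may be concluded. A report that gains in maximal cardiac output, or in maximal extraction, accompanied the gain in ventilation or aerobic capacity would have no direct measurement behind it. Section III says the project is to prepare for a larger study, so a mechanistic claim of this kind could be carried forward.

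**Working it through.** The plan states no figure on this point, and the check needs no power or sample-size calculation. It consists of a count, the plan's own Fick relation, and a look at what an extrapolation would require.

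**1. Count of manoeuvres per training participant**

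Inputs: 2 time points and 2 cardiac output tests at each (Study Assessments); 2 manoeuvres at rest and 2 at target heart rate (Cardiac Output Row Testing).

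- Cardiac output tests: 2 × 2 = 4.
- Manoeuvres: 4 × (2 + 2) = 16, of which 4 × 2 = 8 are at rest, 4 × 2 = 8 are at the 80% target and 0 are at maximal effort.
- If the manoeuvre counts are meant per time point: 2 × (2 + 2) = 8, of which 0 are at maximal effort.
- VO₂max tests: 2 × 2 = 4, with 0 manoeuvres scheduled. That section assigns the device to expired gas analysis.

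The maximal count is zero on either reading.

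**2. Can the VO₂max test supply the missing values?**

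The plan's relation, applied at peak, is VO₂max = CO_peak × (a-v difference)_peak. One quantity is measured and two are unknown. A given gain in VO₂max could come entirely from output, entirely from extraction, or from any mix, and Aim 2 needs the two separated.

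**3. Can peak oxygen uptake be divided by cardiac output from the 80% bout?**

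The plan does not say which oxygen uptake enters the calculation. Taken from the same bout, the result is a submaximal difference. Dividing peak uptake by submaximal output mixes intensities and overstates the difference whenever output is higher at peak. As an illustration, assume that stroke volume is the same at 80% and at peak (not in the documents). Then CO_peak = CO_80 / 0.8 = 1.25 × CO_80, and the mixed ratio is 1.25 times the true peak difference.

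**4. Can the 80% value be extrapolated?**

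No rule is given. Each test yields two levels, rest and 80%. A straight line through two levels fits exactly and leaves 2 − 2 = 0 degrees of freedom to check linearity.

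**The case against.** The strongest reply is that measurement in the graded test was intended and only its description is unfinished. The same device is used in the VO₂max test with a pointer to later details, and the remark that rebreathing does not need a steady state has little purpose if the only use is a steady-state bout. This is fair evidence of intent. It does not put a manoeuvre into the schedule: staff following the text would not know when to perform one, or how many. That reading also requires a change to the plan.

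A second reply is that the 80% data are indirect evidence about the maximum. Heart rate is recorded in the VO₂max test. If stroke volume were constant from 80% to peak, and the target used the peak heart rate from the same time point and NIV condition, peak output would be 1.25 times the measured value, and correlations of changes in output would be unaltered. This too has some force, but it rests on an unstated assumption. If stroke volume differs by ±10%, the multiplier runs from 1.25 × 0.9 = 1.125 to 1.25 × 1.1 = 1.375. If that ratio itself shifts with training, for example from 1.0 to 1.1 with the 80% value unchanged, true peak output rises by 1.375 / 1.25 − 1 = 10% while the scaled estimate shows no change.

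A third reply concerns scope and weight. Section VI does not use the word maximal, and this is a pilot with a correlational aim. Section III is ambiguous: its adjective may govern the first item only or the whole list, and on the second reading the conflict reaches section III as well. None of this removes the conflict between Aim 2 and the procedure.

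**Conclusion.** The concern holds. Aim 2 names a maximal quantity, and the schedule delivers resting and submaximal values with no maximal measurement and no rule for deriving one. The count at maximal effort is 0 of 16 manoeuvres per participant (0 of 8 on the alternative reading). This rests on the text as written and on no assumed effect size.

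The damage is limited to Aim 2. Conclusions about cardiac output and arteriovenous difference at rest and in the 80% bout remain available, and Aims 1 and 3 do not depend on these measurements. That maximal applies to the arteriovenous difference as well as to cardiac output is the natural reading of Aim 2; the conflict over cardiac output does not need it. The point should be corrected, because it changes what the trial may claim.

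**What to change.** Reconcile section II (Aim 2), the VO₂max and Cardiac Output Row Testing procedures in section V, and section VI.

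The least costly change is to restate Aim 2 and the section VI variables as cardiac output and arteriovenous difference in the bout at 80% of peak heart rate, and to limit conclusions to that level. It needs no new visit, device or measurement. Its price is the question about maximal determinants.

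If the investigators meant maximal values, one of two additions is needed, and the choice is theirs:

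- Schedule the rebreathing measurement in the graded test, with a rule for its timing. This adds burden (section VII lists breathlessness during cardiac output measurement as a risk), and the manoeuvre may miss the 30-second peak, which is known only afterwards.
- Prespecify an extrapolation to maximum and state its assumptions. With two measured levels per test, linearity could not be checked from these data.

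Whichever route is taken, it would help to state which peak heart rate sets the target at each cardiac output test (by time point and NIV condition). The plan should also say that the arteriovenous difference uses oxygen uptake from the same bout. These are clarifications; the finding does not rest on them.

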PARTNERS HUMAN RESEARCH COMMITTEE
DETAILED PROTOCOL

PROTOCOL TITLE:

Ventilatory Support to Improve Exercise Training in High Level Spinal Cord Injury

10/17/2017

I. BACKGROUND AND SIGNIFICANCE

The cardioprotective effect of regular aerobic exercise in the general population is broadly accepted, but its importance for those with spinal cord injury (SCI) may be even greater.¹ Although regular aerobic exercise with sufficient intensity and duration can improve overall health, daily energy expenditure is low in those with SCI, due to lack of both motor function and options for accessible physical activity. To overcome this, we developed a unique form of exercise for those with SCI that specifically mirrors exercise performed by the able-bodied. Functional Electrical Stimulation Row Training (FESRT) couples volitional arm and electrically controlled leg exercise,² increasing the active muscle and resulting in the benefits of large muscle mass exercise. We have found improvements in peak aerobic capacity of up to 50% with FESRT in these patients.² However, despite the potential for enhancing aerobic capacity, those with high level lesions (C4 to T4) have the greatest denervation of pulmonary muscle and our preliminary work suggests this limits the aerobic capacity that can be achieved with FESRT. Despite the ability to train the denervated leg skeletal muscle via hybrid FES exercise, the inability to increase ventilation beyond limits set by high level SCI restricts aerobic capacity.

Respiratory restriction in SCI reduces inspiratory capacity in direct relation to lesion level,³ and those with high level injuries have the greatest compromise. As a result, the increase in ventilatory requirements with FES training results in an imbalance between ventilatory capacity and greater whole body skeletal muscle demand after FESRT. Hence, external ventilatory support could improve the ability to exercise train and hence enhance the adaptations to chronic exercise in high level SCI. In obstructive and restrictive pulmonary disorders, non-invasive ventilation (NIV) during exercise training can enhance exercise tolerance^{4,5} and improve gains in exercise capacity.^{6,7} Therefore, we hypothesize that the use of NIV during FESRT will reduce ventilatory limits to exercise, leading to greater exercise tolerance and increased aerobic capacity in high level SCI.

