This pilot project will employ a simple and straightforward statistical approach to compare changes within and between groups. Statistical significance will be set at 0.05, and power at 80%. Normality and equality of variance will be assessed using tests of skewness and kurtosis. Within and between group (FESRT+NIV vs. FESRT+shamNIV) comparison of changes will be made using a general linear model accounting for potential baseline differences and the intervention effect. Correlations between ventilation, aerobic capacity, and hemodynamics variables (cardiac output and arteriovenous oxygen difference) will be assessed by Pearson's or Spearman's coefficient depending on the normality of the variables. If significant relations are found, appropriate regression analyses will be employed.

VII. RISKS AND DISCOMFORTS

Moderate risks are associated with exercise testing and exercise training. Some discomfort and feeling of fatigue will be experienced during these tests. There are other risks associated with these tests including abnormal blood pressure responses, fainting, irregular, fast or slow heart rhythm, and in rare instances, heart attack, stroke, or death. Wearing the face-mask during the VO₂max testing and FES-row training may cause feelings of claustrophobia. Exercise training may induce some muscle or joint discomfort when beginning an exercise program and could result in tendonitis and/or musculoskeletal overuse injuries over time. Subjects may feel lightheaded or short of breath during use of the NIV machine and during the cardiac output measurement. The electrical stimulation unit can cause tingling, pins and needles sensations on the skin, skin irritation, increased muscle spasticity and autonomic dysreflexia (signs include: headache, nausea, rise in blood pressure, sweating, and goosebumps). There is some discomfort with the lancet used on the finger for lactate measurement and there is a small possibility of swelling and bruising at the site(s), there is also a slight chance that individuals become dizzy and even faint. Subjects may feel lightheaded or short of breath during the pulmonary function tests, there is also a slight chance that individuals become dizzy and even faint.

VIII. POTENTIAL BENEFITS

Volunteers will have the opportunity to participate in a supervised exercise program, which may

improve their overall cardiovascular fitness and endurance during activities of daily living as well as decrease risk of chronic disease.

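### Does the Aim 1 analysis need rewriting because it names neither its covariates nor the VO₂max test condition, and gives no basis for 80% power?

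*Combined protocol and SAP*

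**What the plan says.** Section II sets Aim 1: "To determine the magnitude of improvement in aerobic capacity after 3 months of FESRT+NIV compared to FESRT+shamNIV in high level spinal cord injury". Section III randomises thirty people with lesions at T4 or above. It gives no allocation ratio and describes no stratification by lesion level. It adds: "This project will determine the feasibility and effectiveness of this approach to exercise", as groundwork for a larger study.

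Section V (Study Assessments) schedules the tests at baseline and at three months: "There will be 2 separate FES-VO₂max row tests" at each time point, and "Both NIV Support and Sham-NIV groups will perform tests with and without use of the NIV-machine".

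Section VI is the whole statistical plan and describes the project as a pilot. Within- and between-group "comparison of changes will be made using a general linear model accounting for potential baseline differences and the intervention effect". On error and power it says "Statistical significance will be set at 0.05, and power at 80" per cent. It gives no target difference, SD, sidedness or dropout rate.

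On lesion level, section I says "Respiratory restriction in SCI reduces inspiratory capacity in direct relation to lesion level". Section III raises dependence on injury level only for the cross-sectional testing group.

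**The concern.** Three things are left open, and each could matter in a trial of thirty.

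- **Test condition.** Each participant has two VO₂max values per time point. Section III reports that aerobic capacity was higher with NIV at baseline in the first four subjects, so the two values are not interchangeable. An analyst free to choose could report the more favourable one. A change taken from an unassisted baseline to an assisted follow-up would also seem to mix the acute effect of the machine (Aim 3) with the training effect (Aim 1).
- **Covariates.** Adjustment for unspecified baseline differences could be settled after the data are seen. Lesion level, which the Background treats as physiologically important, is not named.
- **Power.** An 80% figure with nothing behind it could lead a reader to take a non-significant result as evidence that NIV does not work, especially as the protocol speaks of determining effectiveness.

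At stake are the false-positive rate of the main comparison and the interpretation of a null result.

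**Working it through.** **Inputs.** From the documents: 30 randomised (section III); significance level 0.05 and power 80% (section VI); two VO₂max tests per time point in both arms (section V). Assumed, because the documents do not say: 1:1 allocation (15 per arm), two-sided testing, pre/post correlation 0.6–0.9, correlation between the two tests 0.5–0.9, and lesion level explaining 0–30% of residual variance.

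**1. The stated 80%.** It cannot be reproduced, because no difference or SD is given. Solved in reverse at 15 per arm:

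d = (1.960 + 0.842) × √(2/15) = 1.02 SD of the change (normal approximation), or 1.06 SD with the noncentral t.

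With 12 completers per arm the t-based value is 1.20 SD. At 15 per arm, power is 26% for d = 0.5, 56% for 0.8, 75% for 1.0 and 89% for 1.2. So the 80% holds for effects of about 1.06 SD or more. The documents give no figure that shows whether this is too optimistic. Under a model with baseline and lesion level, the detectable difference is 1.104 residual SD. In raw VO₂max SD that is 1.104 × √(1 − r²), or 0.88, 0.79, 0.66 and 0.48 for pre/post correlation r = 0.6, 0.7, 0.8 and 0.9. A value above 1 residual SD therefore does not by itself show an underpowered trial.

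**2. Error if the test is chosen by its p-value.** For two independent tests the upper figure is 1 − 0.95² = 9.75%. In 40,000 simulated null trials, the chance that at least one test is significant was 9.0%, 8.2% and 7.1% at between-test correlations of 0.5, 0.7 and 0.9. Across 27 settings of the assumed ranges (50,000 null trials each), taking the smallest p gave:

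| What is chosen by smallest p | Type I error |
|---|---|
| Nothing: one fixed model | 4.8–5.2% |
| Adjustment (with or without lesion level) | 5.6–7.7% |
| Test condition | 7.0–9.4% |
| Both | 8.3–13.4% |

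The last three rows all require deliberate selection on p. The first row is what any single model delivers.

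**3. Mixing conditions.** Let a be the mean acute effect of support at testing, and T_N and T_S the training effects in the two arms. A change from unassisted baseline to assisted follow-up has mean a + T_N in the NIV arm and a + T_S in the sham arm. The between-arm difference is (a + T_N) − (a + T_S) = T_N − T_S. The acute effect drops out if support at testing is the same in both arms and training does not alter the acute response. It would distort the within-group changes. The plan does not need such a contrast, since both conditions are measured at both time points.

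**4. Adding lesion level.** The detectable difference at 80% power is 1.081 residual SD with baseline VO₂max alone. It becomes 1.104 with an uninformative lesion term, a rise of 1.104/1.081 − 1 = 2.1% (2.8% at 12 per arm: 1.262/1.228 − 1). Break-even is at R² = 1 − (1.081/1.104)² = 4.1% at 15 per arm, and 1 − (1.228/1.262)² = 5.3% at 12. If lesion level explained 10% or 30%, the difference would be 1.104 × √0.9 = 1.047 or 1.104 × √0.7 = 0.924. Those are 3.1% and 14.6% below 1.081.

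**The case for a change.** The strongest case for a change is that it would cost only words. The two VO₂max tests answer different questions (capacity unassisted, or capacity while supported), and a significance test at 0.05 is planned on an outcome meant to justify a larger trial. The pilot label softens the power point, but not an undeclared choice of outcome. Naming one condition and one covariate list would hold the error near 5%.

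Much of this stands. No section designates the test or lists the covariates, and a reader cannot confirm from the protocol that the choice preceded the data. Section V also does not say whether the sham arm's test with the machine uses sham or active pressure, and the cancellation shown above depends on that.

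The rest is weaker. In a model of changes, adjustment for baseline differences is most naturally read as adjustment for the baseline value of the outcome, with follow-up paired to the same test. The upper end of the inflated error needs a between-test correlation of 0.5, a lesion effect of 30% and selective reporting, all supplied by assumption.

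Lesion level is a matter of judgement. Eligibility already narrows its range ("inclusion criteria are SCI at neurological level" T4 or above), and baseline VO₂max may carry part of its influence. The dependence on injury level raised in section III concerns effect modification in a different group, which a main-effect term would not address. Rewriting the model sentence as a VO₂max-only ANCOVA would also drop the planned within-group comparisons and the model for ventilation, cardiac output and arteriovenous oxygen difference.

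**Conclusion.** No change is needed. The plan is short on detail, but the model it describes gives a sound answer when applied in the ordinary way: change in VO₂max between arms, adjusted for baseline from the same test, with error near 5%. An analyst can show the result for both conditions and let readers see whether they agree. The 7–9% (test chosen) or 8–13% (test and adjustment chosen) describes selective reporting under assumed correlations and 15 per arm, not a consequence of what is written.

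Whether to include lesion level is a fair trade-off at this size: a 2.1% loss if it is uninformative, against a gain of 3–15% if it explains 10–30% of residual variance, with nothing in the documents to place it on that scale. The 80% is unsupported but not shown to be false. It matches an effect of about 1.06 SD of the change, and substituting residual-SD figures would still supply no VO₂max difference or SD. A null result from a pilot of this size should be read through its confidence interval in any case.

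The conclusion would weaken if support during testing differed between arms and only the assisted test were reported. The documents leave the sham arm's test setting unstated but do not indicate that such an analysis is intended.
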